4.5 INFUSION REACTIONS

Patients receiving rituximab, particularly those with high concentrations of circulating malignant cells, commonly have infusional toxicities including fever, chills, nausea and vomiting, dyspnea, hypotension, and palpitations. Infusional reactions with rituximab have been observed in HCL as well as other malignancies and are best managed by slowing or interrupting the rate of infusion.

5 DATA COLLECTION AND EVALUATION

5.1 DATA COLLECTION

The PI will be responsible for overseeing entry of data into a 21 CFR Part 11-compliant data capture system provided by the NCI CCR and ensuring data accuracy, consistency and timeliness. The principal investigator, associate investigators/research nurses and/or a contracted data manager will assist with the data management efforts. Primary and final analyzed data will have identifiers so that research data can be attributed to an individual human subject participant.

Patients treated both inside and outside of NIH will require source documentation regarding dosage and timing of drug administration. For patients treated outside NIH, results of lab, radiology and pathology tests should be faxed to the PI

All adverse events, including clinically significant abnormal findings on laboratory evaluations, regardless of severity, will be followed until return to baseline or stabilization of event.

Document AEs from the first study intervention, Study Day 1, through 30 days after the end of treatment. Beyond 30 days after the last intervention, only adverse events which are serious and related to the study intervention need to be recorded.

An abnormal laboratory value will be recorded in the database as an AE **only** if the laboratory abnormality is characterized by any of the following:

- Results in discontinuation from the study
- Is associated with clinical signs or symptoms
- Requires treatment or any other therapeutic intervention
- Is associated with death or another serious adverse event, including hospitalization.
- Is judged by the Investigator to be of significant clinical impact
- If any abnormal laboratory result is considered clinically significant, the investigator will provide details about the action taken with respect to the test drug and about the patient's outcome.

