
1.3.3 Inability to assume that rituximab should be used with cladribine

Before a trial begins it is optimal for neither arm of a randomized trial to be obviously more advantageous than the other. There are potential advantages and disadvantages of simultaneous vs. delayed rituximab. It is possible, for example, that rituximab could have been more effective when begun at least 6 months after cladribine than concurrently, because by that time masses of tumor cells in the marrow, spleen and lymph nodes, which would present a tumor penetration problem for the rituximab Mab, might be at their minimum size. Secondly, if simultaneous rituximab were to fail to eliminate MRD, it could select for cells deficient in apoptosis and render patients unresponsive to rituximab and other agents when relapse occurs later in the disease course. Moreover, it is possible that the risk of infection could increase with combined use of rituximab and cladribine, since rituximab is known to cause rapid and prolonged (3-6 month) depletion of normal B-cells [57]. While this may not be a significant problem after single-agent short-course rituximab, it may be more problematic with the longer 8-cycle course, particularly after cladribine. Thus, a randomized trial was needed to determine if rituximab should be used with cladribine or delayed until after MRD appears. At this time, it is not considered standard to combine rituximab with cladribine for first-line or second-line treatment of HCL.

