2.3.2 Treatment Assignment and Randomization Procedures

Cohorts

Number	Name	Description
1	Cohort 1	Patients with HCL with (62 patients) and without (68 subjects) prior course of purine analog to be randomized between Arm 1 and Arm 2 (randomization stratified based upon prior purine analog [yes/no])
2	Cohort 2	Patients with HCL without prior course of purine analog to be directly assigned to Arm 3 (25 patients; after completion of the 68 patients without prior purine analog in Cohort 1)
3	Cohort 3	Patients with HCLv to be directly assigned to Arm 3 (20 patients)

Arms

Number	Name	Description
1	Arm 1	Cladribine + Rituximab
2	Arm 2	Cladribine (+ Rituximab after 6 months if MRD detected)
3	Arm 3	Cladribine + Rituximab (Rituximab will be administered just before rather than after the 1 st of the 5 daily doses of cladribine on day 1)

Stratifications

Name	Distinct Options	Notes

Prior purine analog	Yes No	Applies to Cohort 1 patients randomized between Arm 1 and Arm 2 only (see below).
---------------------	-----------	---

Randomization and Arm Assignment

At the time of registration, patients in Cohort 1 will be randomized between Arm 1 and Arm 2, and patients in Cohort 2 will be directly assigned to Arm 3. Patients with variant HCL (HCLv; Cohort 3) regardless of prior treatment with purine analog are assigned to Arm 3.

- Cohort 1: HCL Patients will be randomized between Arm 1 and 2. Randomization will be stratified on the basis of prior purine analog or not. There will be 68 patients randomized within the no prior purine analog stratum and 62 randomized within the 1+ prior purine analog stratum.
 - Note: The randomization for Cohort 1 will be performed by CRO personnel using randomization assignments generated by the study statistician. The Pharmacy Department will be notified of the treatment assignment once the patient is randomized.
- Cohort 2: 25 patients with no prior purine analog will be assigned directly to Arm 3 following completion of randomization of the 68 patients in the ‘no prior purine analog’ stratum in Cohort 1.
- Cohort 3: Patients with variant HCL (HCLv) regardless of prior treatment with purine analog will be enrolled in this cohort, will not be randomized and will be assigned to Arm 3.

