3.2 DRUG ADMINISTRATION

3.2.1 Cladribine

Cladribine 0.15 mg/Kg/day by 2-hour i.v. infusion days 1-5. The infusion time may be changed to 1 hour at the discretion of the PI.

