3.2.2 Rituximab

Rituximab 375 mg/m² i.v. infusion every week x8, begin day 1 in half of randomized patients and in all HCLv patients, and then again in all patients at least 6 months later when HCL is detected by blood FACS. Patients who first received rituximab at least 6 months after cladribine may receive a 2nd course of rituximab at the same dose and schedule at least 6 months after the beginning of the 1st course, if and when HCL is detected again by blood FACS. When rituximab is given on the same day as cladribine (day 1), it will be given at the end of the 2-hour infusion of cladribine. In the 25 nonrandomized newly-diagnosed HCL patients beginning rituximab prior to cladribine, the 2 hour infusion of cladribine will be begin at the end of the infusion of rituximab. Actual body weight measured within 4 weeks prior to initial treatment with rituximab will be used for calculations of body surface area.

It is possible, though uncommon for HCL and HCLv to change phenotype. This would be considered a second malignancy which would require patients to be taken off-treatment. However, we feel it is justified for these patients to remain on study and continue to receive treatment despite the development a new clone (second malignancy) because they are likely to receive on-going benefit from the treatment. Thus, at the discretion of the PI, these patients may continue with treatment including delayed Rituximab if appropriate.

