3.3 TREATMENT MODIFICATIONS

3.3.1 Treatment Delay

- Dosing of cladribine may be delayed up to 2 weeks, rituximab up to 12 weeks for toxicity or logistical reasons, including inability of the patient to get to clinic. The one week interval between rituximab doses may also be shortened by one day for logistical reasons.
- Patients with excessive delay or dose-limiting toxicity (DLT) are off-treatment and may be followed but not retreated.
- Infusions should be discontinued in the event of serious or life-threatening cardiac arrhythmias. Subjects who develop clinically significant arrhythmias which are not dose-limiting should undergo cardiac monitoring during and after subsequent infusions.

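### Full adverse-event recording ends at about day 80 in Arm 1 and day 35 in Arm 2, so any by-arm safety summary needs a common time window

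*Combined protocol and SAP*

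**What the plan says.** Section 5.1 (Data Collection) gives the recording rule: "Document AEs from the first study intervention, Study Day 1, through 30 days after the end of treatment". For later events it says: "Beyond 30 days after the last intervention, only adverse events which are serious and related to the study intervention need to be recorded". The period therefore follows each patient's last dose and not a fixed time from randomization.

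The two randomized arms finish initial treatment at different times. Section 3.2.1 gives "Cladribine 0.15 mg/Kg/day by 2-hour i.v. infusion days 1-5". Section 3.2.2 gives rituximab as "i.v. infusion every week x8, begin day 1 in half of randomized patients". Section 2.3.2 describes Arm 2 as "Cladribine (+ Rituximab after 6 months if MRD detected", so some Arm 2 patients have a second treatment period long after the first. Neither the end of treatment nor the last intervention is defined for them. Section 5.1.1 calls for a fresh baseline before delayed rituximab. That points to a course-by-course reading but does not state one.

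Section 1.3.3, in arguing that a randomized trial was needed, notes that "it is possible that the risk of infection could increase with combined use of rituximab and cladribine". It also cites normal B-cell depletion lasting 3 to 6 months after rituximab.

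**The concern.** When arms are observed for different lengths of time, the arm watched longer collects more events even if the underlying rates are equal. Here the longer-watched arm is the one whose infection risk Section 1.3.3 questions, so an excess in a crude table could be read as a harm of concurrent rituximab when part of it is extra recording time. Section 1.3.4 foresees that the trial may lead to a recommendation to make the combination standard. Weighing benefit against harm for that purpose needs harms data that can be compared between arms.

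The events required after the window closes do not fully repair this. They must be both serious and judged related, and no blinding or placebo is described, so that judgement is made with the treatment known. Supplier reporting of all serious events regardless of cause (Section 11.1) starts at first exposure to rituximab. It covers Arm 1 from day 1, but not an Arm 2 patient before delayed rituximab.

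**Working it through.** The documents give no window length in days and no power for a safety comparison, so there is no stated figure to reproduce.

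**Window lengths (initial course, on schedule)**

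- Arm 1: eight weekly doses from day 1 put the last dose on day 1 + 7 × 7 = 50. Adding 30 gives day 80.
- Arm 2: the last cladribine dose is on day 5. Adding 30 gives day 35.
- Difference: 80 − 35 = 45 days. Ratio: 80/35 = 2.29.

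Section 3.3.1 allows delays: "Dosing of cladribine may be delayed up to 2 weeks, rituximab up to 12 weeks for toxicity or logistical reasons". With one maximum delay in each arm, the windows become 50 + 84 + 30 = day 164 and 5 + 14 + 30 = day 49.

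**The other reading.** If the end of treatment means the last protocol therapy of any kind, patients who never need delayed rituximab still have about day 80 and day 35. Patients who do need it have a much longer window, and its length depends on when residual disease is found, which is itself an outcome. This reading does not equalise the arms either.

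**Size of the artefact (illustration)**

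Assumptions: the true event process is the same in both arms; incidence by day 35 is *p* = 13%; the hazard on days 36 to 80 is a fraction *f* of the constant hazard on days 1 to 35. The 13% is borrowed from the historical infection rate after cladribine in Section 1.2.1, which comes without a time window.

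Recorded incidence in Arm 1 = 1 − (1 − *p*)^(1 + *f* × 45/35).

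| *f* | Exponent | Arm 1 recorded | Arm 2 recorded | Ratio |
|---|---|---|---|---|
| 0.25 | 1.321 | 16.8% | 13% | 1.29 |
| 0.50 | 1.643 | 20.5% | 13% | 1.57 |
| 1.00 | 2.286 | 27.3% | 13% | 2.10 |

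With *p* from 5% to 42% and the same three values of *f*, the ratio runs from 1.22 to 2.21. As *f* approaches 0 the ratio approaches 1.

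To put this on a familiar scale, suppose someone applied a two-sided 0.05 Fisher test to these crude counts with 34 + 31 = 65 patients per arm. At *p* = 13% it would falsely favour Arm 2 in 5.6%, 14.7% or 45.0% of trials for the three values of *f*, against 1.4% with equal windows. The plan does not propose such a test.

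**The case against.** A reader might infer that the trial's planned safety comparison is biased. The documents do not support that. The secondary objectives (Section 1.1.2) and the statistical section (6.1 to 6.3) contain no toxicity or infection comparison of Arm 1 with Arm 2. The toxicity comparison that is described sets rituximab first against cladribine first (Sections 1.3.5 and 3.1.1). Both of those groups receive eight weekly doses and share the window of about 80 days. This objection stands: what is at risk is a descriptive summary.

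A reader might also infer that Arm 2 goes unobserved after day 35. It does not. Serious related events are still required in both arms, with no stated end date, so the gap concerns events that are not serious or are judged unrelated. Late infections missed under the rule are a limit on what is captured in both arms. They are not in themselves evidence of bias between arms.

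It is tempting to say that Arm 1 counts will be 2.3 times those of Arm 2. That needs a constant event rate to day 80. The protocol expects many events early: it places severe infusion reactions mainly at the first infusion (Section 1.2.6) and calls febrile neutropenia common after cladribine (Section 4.1). A lower multiple is therefore plausible, and it could be near 1.

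Finally, day 35 is an inference from an undefined term. That is fair, but the alternative reading does not give equal windows, so the ambiguity is part of the problem and not an answer to it.

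**Conclusion.** The point holds in a limited form. The recording rule leaves its own end point undefined for patients who may receive delayed rituximab. On the better-supported reading by initial course, it gives scheduled windows of about 80 and 35 days in the two randomized arms. A crude by-arm summary of adverse events or infections could then overstate Arm 1: about 17% to 27% against 13% under the assumptions above, with no true difference. The size depends wholly on how many events fall between days 36 and 80, which the documents do not tell us.

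The 6-month primary endpoint is untouched, and no planned test is invalidated. The change is worth making because infection risk is one of the protocol's own reasons for randomizing and the remedy is cheap.

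**What to change.** 1. In Section 5.1, define the recording period for each treatment course: the initial course and each course of delayed rituximab.
2. State that any safety summary of Arm 1 against Arm 2 uses one common calendar window from day 1. For data already collected, use days 1 to 35, or report by equal time intervals within which both arms were fully recorded.
3. For patients still to be followed, record all adverse events in both randomized arms to the same fixed time, for example the 3-month contact, and infections to the 6-month visit. The 3-month contact may move by 2 weeks (Appendix A), so cut the summary at a fixed study day and not at the contact date.

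With equal windows the ratio of observation time is 1.0 and the artefact is removed.

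**Cost.** After week 5 the calendar has no history and physical until 6 months. Week 9 lists only a blood count, and 3 months lists only blood tests. An adverse-event query would have to be added at both contacts. A summary limited to days 1 to 35 needs no new data but contains fewer events and says nothing about later infections. Section 6.3.1 already reports residual-disease results for 27 concurrently treated patients, so for part of the trial only the analysis change in step 2 is available.

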5.1.1 Protocol Specific Details to be Considered

- Best response to cladribine with or without immediate rituximab, and to each course of delayed rituximab
- Dates of achievement of CR (onset and relapse) and PR
- Dates of MRD negativity (onset and relapse) for flow cytometry of the blood and bone marrow, and immunohistochemistry of the bone marrow biopsy
- Dates of death for determination of overall survival
- A preexisting (baseline) laboratory abnormality will be considered the last one obtained prior to the first dose of drug (cladribine or delayed rituximab), unless the PI considers an abnormality of higher grade occurring within 100 days prior to the first dose to be a truer baseline
- Calcium values corrected for albumin will be used to report hypocalcemia

- Baseline signs and symptoms prior to enrollment cannot serve as the baseline for delayed rituximab courses, since baseline events likely resolve during the >6 months before delayed rituximab, and events occurring after delayed rituximab may no longer be due to disease

End of study procedures: Data will be stored according to HHS, FDA regulations, and NIH Intramural Records Retention Schedule as applicable.

5.2 RESPONSE CRITERIA

5.2.1 Tests needed for response assessment

- Blood tests: CBC, flow cytometry
- CT scan or other imaging study if abnormal prior to cladribine
- BMBx with immunohistochemistry, and BMA

5.2.2 Time intervals for restaging

- See Section 15, Study Calendar

5.2.3 Rules for response assessment

- No G-CSF or GM-CSF at least 4 weeks before major response.
- No transfusions at least 4 weeks before major response.
- Hgb requirement for major response may be dropped if iron stores are low (ferritin ≤ 20)
- Isolated low blood counts do not indicate relapse unless they are consistently low, i.e., at least 2 low counts > 1 week apart.
- A minimum duration of response is not required.

5.2.4 Complete remission (CR): All of the following:

- Absolute neutrophil count (ANC) $\geq 1500/\mu\text{l}$
- Platelets $\geq 100,000/\mu\text{l}$
- Hgb $\geq 11 \text{ g/dl}$
- Spleen non-palpable or not below costal margin on CT.
- Circulating HCL cells non-visible on Wright stain
- Lymph nodes $\leq 2 \text{ cm}$ (short axis)
- Absence of hairy cells on BM aspirate smears and bone marrow biopsy by H&E and Wright stains.
- CR with MRD in the BMBx by IHC is defined as CR and a ratio of B cells to T cells of at least 1, and most of the B cells having characteristics consistent with HCL.

- CR with MRD in the peripheral blood is defined as CR and a positive peripheral blood FACS or PCR.
- Patients meeting all criteria for CR except minimum levels of ANC, platelets and Hgb will be considered CR if MRD is absent by BMBx IHC and by flow cytometry of blood and bone marrow.

5.2.5 Partial Response (PR): All of the following:

- Neutrophils $\geq 1,500/\mu\text{L}$ or 50% improvement over baseline.
- Platelets $\geq 100,000/\mu\text{L}$ or 50% improvement over baseline.
- Hgb $\geq 11.0 \text{ g/dL}$ or 50% improvement over baseline. For patients who are transfusion-dependent at baseline, Hgb of $\geq 9.0 \text{ g/dL}$.
- $\geq 50\%$ decrease in circulating malignant HCL count from the pretreatment baseline.
- $\geq 50\%$ reduction in sum of products of perpendicular diameters or decrease to $\leq 2 \text{ cm}$ (short axis) in evaluable ($> 2\text{cm}$) lymphadenopathy.
- $\geq 50\%$ reduction in extent of spleen below costal margin by CT or physical exam, if abnormal at baseline.

5.2.6 Progressive disease (PD): Any of the following:

- $\geq 50\%$ increase in sum of products of perpendicular diameters of evaluable ($> 2\text{cm}$) lymphadenopathy or appearance of new evaluable lymph nodes $> 2 \text{ cm}$.
- $\geq 50\%$ increase in extent of spleen below costal margin by CT or physical exam, if abnormal at baseline.
- $\geq 50\%$ increase in the absolute number of circulating malignant lymphocytes.

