4 SUPPORTIVE CARE

4.1 INFECTIONS/FEVER AND NEUTROPENIA

Febrile neutropenia is a common side-effect of cladribine which require empiric antibiotics, either as an inpatient or outpatient. Hematopoietic growth factors may be used if clinically indicated. Fever is also common with rituximab and may be treated symptomatically and with interrupting or with decreasing the infusion rate, as detailed in Section 13.2.6. Patients may receive prophylactic valacyclovir and less commonly prophylactic Bactrim if judged by the PI to be at significant risk of Herpes Zoster and Pneumocystis infections, respectively. Generally, prophylaxis will extend from the beginning of cladribine treatment until at least the 3-month time point when reassessments of CD4 and other blood counts are possible. If they have an allergy to Bactrim, Pentamidine or other medications/treatments may be ordered instead. Pneumocystis is extremely rare in HCL, particularly in newly diagnosed patients, allowing its prophylaxis to be reserved for patients with high risk, for example with very low CD4 counts or a prior history of infection.

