4.2 BLOOD PRODUCT SUPPORT

Symptomatic anemia should be treated with appropriate red blood cell support. Transfusion is generally recommended if the hemoglobin falls below 8g/dL, but lower levels are acceptable particularly for younger patients. Recombinant erythropoietin may also be used. Platelets are generally given when the platelet count is < 10,000/mm³ or when there is bleeding.

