purine analog and the 62 HCL patients with 1 prior courses of purine analog will be randomized. Based on data in the literature and data from prescreening LMB patients, out of 31 HCLv patients a historical CR rate 3% (1/31) and ORR of 35% (11/31) may be assumed from cladribine alone. If 20 patients are enrolled, and if there are 3 or more CRs in the 20 patients, there is only 7.5% probability this would occur if the true complete response rate were 5%; there is a 90.9% probability that this would occur if the true complete response rate were 25%. Thus, observing 3 or more CRs in 20 patients would provide strong evidence that the true complete response rate was consistent with 25% and more than 5%. If 20 patients are enrolled, and if there are 11 or more responses in the 20 patients, there is only 5.3% probability this would occur if the true response rate were 35%; there is an 87.8% probability that this would occur if the true response rate were 65%. Thus, observing 11 or more responses in 20 patients would provide strong evidence that the true response rate was consistent with 65% and more than 35%.

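### The 4-week support-free rule for response in section 5.2.3 omits erythropoietin, which section 4.2 permits, so a drug-supported hemoglobin can count toward PR and, in some patients, CR

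*Combined protocol and SAP*

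**What the plan says.** Section 5.2.3 has two rules that keep supported counts from being credited as response: "No G-CSF or GM-CSF at least 4 weeks before major response" and "No transfusions at least 4 weeks before major response". Its one provision specific to hemoglobin is a relaxation: "Hgb requirement for major response may be dropped if iron stores are low" (ferritin 20 or below). It also states that a response needs no minimum duration.

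Section 4.2, in its paragraph on anemia, says: "Recombinant erythropoietin may also be used". It sets no time limit relative to response assessment.

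Hemoglobin enters the response definitions as follows:

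- **CR (5.2.4):** at least 11 g/dL. There is a waiver: "Patients meeting all criteria for CR except minimum levels of ANC, platelets and Hgb will be considered CR if MRD is absent" by marrow biopsy IHC and by flow cytometry of blood and marrow.
- **PR (5.2.5):** at least 11.0 g/dL or a 50% improvement over baseline, or at least 9.0 g/dL for a patient who was transfusion-dependent at baseline.

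Section 6.2 reports CR and PR rates with exact 95% confidence intervals. It reads the 20-patient HCLv cohort against fixed counts. For overall response, "observing 11 or more responses in 20 patients would provide strong evidence" that the true rate is above 35%; for CR the count is 3 or more, against a true rate of 5%.

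**The concern.** The plan already accepts that a count raised by support should not be read as recovery from disease. It applies this to myeloid growth factors and to transfusions, but not to erythropoietin, a third form of support that it names itself. No reason for the exemption is given, and no other section excludes or flags a hemoglobin obtained on erythropoietin.

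The patients exposed are those whose response turns on hemoglobin. One example is a patient who is transfusion-dependent at baseline and later receives erythropoietin instead. That patient can satisfy both the 4-week transfusion rule and the 9.0 g/dL PR limit while still supported. Because no minimum duration is required, no later unsupported value has to confirm the response.

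At stake are the reported CR and PR rates and, more visibly, the HCLv counts. These are small integers read against a cut-off, with no concurrent control.

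**Working it through.** **1. Support permitted, set against support covered by 5.2.3**

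| Support | Permitted in | 4-week rule in 5.2.3 |
|---|---|---|
| G-CSF, GM-CSF | 4.3 | Yes |
| Transfusions | 4.2 | Yes |
| Erythropoietin | 4.2 | No |

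Section 4.1 also allows growth factors in general ("Hematopoietic growth factors may be used if clinically indicated"), but in a paragraph on infection and neutropenia. The point therefore rests on the sentence in 4.2.

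**2. Which classifications can change**

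- *Primary endpoint (6.1).* MRD at 6 months is positive if blood FACS, marrow aspirate FACS or marrow biopsy IHC is positive. Hemoglobin plays no part, so nothing changes.
- *CR, MRD absent by IHC and by blood and marrow flow.* The count minimums are waived, so erythropoietin cannot change the classification.
- *CR, other patients.* Status can change only if neutrophils, platelets, spleen, nodes, circulating cells and marrow morphology all qualify and hemoglobin alone would fail.
- *PR.* The waiver does not apply. Status can change if every other PR criterion is met and hemoglobin alone would fail.
- *Secondary MRD status (6.2).* Positive blood FACS is enough for MRD-positive status, and negative FACS in both blood and aspirate gives MRD-negative status whatever the counts. Hemoglobin below 11 can decide only when blood FACS is negative, aspirate FACS is positive or missing, and neutrophils and platelets are not themselves low. The précis further limits low counts to those attributed to HCL.

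**3. The plan's HCLv figures**

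With X ~ Binomial(20, p), the stated probabilities reproduce:

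- CR rule: P(X ≥ 3) = 0.0755 at p = 0.05 and 0.9087 at p = 0.25 (plan: 7.5% and 90.9%).
- Response rule: P(X ≥ 11) = 0.0532 at p = 0.35 and 0.8782 at p = 0.65 (plan: 5.3% and 87.8%).

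**4. What one reclassified patient does at the cut-off**

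- CR at p = 0.05: P(0) = 0.95^20 = 0.3585 and P(1) = 20 × 0.05 × 0.95^19 = 0.3774. So P(X ≥ 2) = 1 − 0.3585 − 0.3774 = 0.264 (from unrounded terms), against 0.0755 for X ≥ 3.
- Response at p = 0.35: P(X = 10) = 0.0686, so P(X ≥ 10) = 0.0532 + 0.0686 = 0.122, against 0.0532 for X ≥ 11.

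An unsupported count of 2 CRs or 10 responses, raised by one, therefore meets the plan's threshold. These figures would be the same for any single misclassification; they do not measure how often this one occurs.

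**5. Illustration under an assumed rate**

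Suppose a share m of all HCLv patients is moved up by supported hemoglobin. The documents give no value, so m from 0 to 5 percentage points is an assumption. The chance of meeting each rule at the null rate becomes P(X ≥ 3) at p = 0.05 + m and P(X ≥ 11) at p = 0.35 + m:

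| m (points) | CR rule | Response rule |
|---|---|---|
| 0 | 0.0755 | 0.0532 |
| 1 | 0.115 | 0.0645 |
| 2 | 0.161 | 0.0775 |
| 5 | 0.323 | 0.1275 |

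For CR, m is a net shift after the MRD-negative waiver, so it is limited to patients outside that waiver.

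**The case against.** The strongest reply is that the gap is real but narrow. The primary comparison does not use hemoglobin. For CR, the waiver removes every patient who is MRD-negative by IHC and flow. For the rest, and for PR, hemoglobin must be the only failing criterion. Section 6.2 labels all evaluations other than the primary comparison exploratory, and no go or no-go action hangs on the HCLv counts. The binomial contrasts show only that a discrete cut-off is sensitive to one patient. All of this stands.

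Two stronger readings are tempting, and the documents support neither.

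- *That supported responses inflate the apparent gain from rituximab over the historical cladribine-alone rates in HCLv.* This would require the historical responses to have excluded erythropoietin-supported hemoglobin. Sections 1.3.12 and 6.2 do not say how they were assessed. If the same permissive rule applied, the effect would partly cancel. Between the randomized arms, erythropoietin is allowed equally and no differential use is shown.
- *That supported hemoglobin broadly hides MRD relapse.* In 6.2 it can matter only in the narrow configuration set out in the working.

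The reply does not supply a rule that covers erythropoietin, or a reason for treating it differently from the two supports already listed.

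**Conclusion.** The point holds as a gap in the secondary response definitions. Section 5.2.3 lets an erythropoietin-supported hemoglobin count toward PR, and toward CR in patients who are not MRD-negative by IHC and by blood and marrow flow, when all other criteria are met. The consequences are confined to the secondary CR and PR rates and the exploratory HCLv counts, where a single patient can decide whether a threshold is met. The primary endpoint, its sample size and its power are unaffected.

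The size and direction of any bias are unknown. They depend on how often erythropoietin was in use when the qualifying hemoglobin was obtained, and on how the historical HCLv responses were judged; the documents give neither. The correction is worth making because it is cheap and follows the plan's own principle, not because a material bias has been shown.

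**What to change.** - In 5.2.3, add erythropoietin to the existing 4-week list, for response classification only. The 4-week period is carried over from the two existing rules for consistency; the documents give no separate basis for it.
- Add erythropoietin start and stop dates to the response data items in 5.1.1, which do not list them.
- For patients already assessed, check the records. Report CR and PR rates, including the HCLv counts, with a sensitivity analysis that reclassifies patients whose qualifying hemoglobin was obtained on erythropoietin.
- For the hemoglobin component of the 6.2 MRD definition, only flag values obtained on erythropoietin in the analysis. Leave the definition itself alone, because 6.2 also uses it to trigger delayed rituximab.

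No change to supportive care or to the delayed-rituximab trigger is proposed, and sample size, power and significance level stay as they are. The cost is a short edit, one more data item and a retrospective records check. A few responses may be dated later or downgraded.
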